4.1.3 Rescreening

A screen failure is a patient who has given informed consent and failed to meet all of the inclusion criteria and/or met at least one of the exclusion criteria and has not been randomized (eg, due to a viral or other active infection, or repeat laboratory test result outside of reference range). Patients who fail their initial Screening will be allowed to present for rescreening once, if approved in advance by the medical monitor. Rescreen requests must be discussed with the medical monitor prior to rescreening the patient, including what has changed about the patient's medical status.

Patients who present for rescreening will be assigned a new Screening number. The investigator or designee will record rescreening data on the source document and the appropriate eCRF. Details for rescreening procedures will be provided in the IRT manual.

4.2 Withdrawal of Patients from the Study

Estimated duration of the study will be approximately 21 weeks, including 1 week of Screening. Patients will be followed up to 20 weeks after the initial treatment.

4.2.1 Reasons for Withdrawal/Discontinuation

Patients may withdraw from the study at any time and for any reason without prejudice to their future medical care by the investigator or at the study site. Every effort should be made to keep patients in the study. The reasons for patients not completing the study will be recorded. A patient may be withdrawn from the study for any of the following reasons:

1. The patient does not meet the protocol inclusion or exclusion criteria at the baseline visit.
2. [REDACTED]

9. The patient withdraws consent.

The investigator will also withdraw a patient if Aeon Biopharma terminates the study. Upon occurrence of a serious or intolerable AE, the investigator will confer with the sponsor. If a patient is discontinued because of an AE, the event will be followed until it is resolved.

4.2.2 Handling of Withdrawals

Patients are free to withdraw from the study or investigational study drug at any time upon their request. Patient participation in the study may be stopped at any time at the discretion of the investigator or at the request of the sponsor.

Term	Percentage (%)
GDP	100
Inflation	100
Interest rates	100
Central bank	100
Monetary policy	100
Quantitative easing	100
Inflation targeting	100
Interest rate hike	100
Interest rate cut	100
Interest rate parity	100
Nominal interest rate	100
Real interest rate	100
Nominal GDP	100
Real GDP	100
Nominal exchange rate	75
Real exchange rate	80
Nominal income	100
Real income	100

It is vital to obtain follow-up data on any patient withdrawn because of an AE or SAE. In every case, efforts must be made to undertake protocol-specified, safety, follow-up procedures.

4.2.3 Replacements

Patients who discontinue prematurely from the study will not be replaced.

5 Study Treatments

5.1 Method of Assigning Patients to Treatment Groups

Patients will be randomly assigned at the baseline visit (Visit 2) to receive ABP-450 low dose (150 units), ABP-450 medium dose (250 units), ABP-450 high dose (350 units), or placebo using a 1:1:1:1 allocation ratio. To ensure balance across the treatment groups, randomization will be stratified by previous treatment with BOTOX® (BOTOX® naïve vs. previously treated with BOTOX® within 4-12 months prior to baseline). [REDACTED]

[REDACTED]

[REDACTED]

[REDACTED]

5.2 Treatments Administered

Investigational study drug is a *Clostridium botulinum* toxin type A

- Investigational study drug vials contain 100 units of lyophilized ABP-450
- Placebo vials contain sodium chloride for injection, USP, 0.9%, preservative-free

The dose to be administered to patients in the study will range between 150 units and 350 units.

Active Treatment Arms	Dose
ABP-450 low dose	150 units
ABP-450 medium dose	250 units
ABP-450 high dose	350 units

[REDACTED]

A large black rectangular redaction box covers the majority of the page content, from approximately y=111 to y=886. The redaction is positioned in the center of the page, with a thin white border around the black area.

5.3 Identity of Investigational Product

ABP-450 is lyophilized powder packed in vials containing 100 units. Placebo will be sodium chloride for injection, USP, 0.9%, preservative-free (from the same lot that is used for reconstitution of the toxin[s]).

11. **What is the primary purpose of the *Journal of Clinical Endocrinology and Metabolism*?**

The following drug supplies will be used in the study:

Product	Supplied as:
ABP-450	100 units of lyophilized powder packed in 10-mL vials
Placebo	Sodium chloride injection, USP, 0.9%, preservative-free, 10-mL vials

5.4 Management of Clinical Supplies

5.4.1 Investigational Study Drug Packaging and Storage

Topic	Percentage
Smart homes	95
Smart cities	95
Smart transportation	95
Smart energy	95
Smart agriculture	95
Smart manufacturing	95
Smart healthcare	95
Smart waste management	95
Smart water management	95
Smart buildings	95
The concept of a 'smart city'	60

5.4.2 Test Article Accountability

The investigator will maintain accurate records of receipt of all test articles, including dates of receipt. In addition, accurate records will be kept regarding when and how much test article is dispensed and used by each patient in the study. Reasons for departure from the expected dispensing regimen must also be recorded. At the completion of the study, to satisfy

regulatory requirements regarding drug accountability, all investigational study drugs will be reconciled and retained or destroyed according to applicable regulations.

5.4.3 Other Supplies

[REDACTED]

[REDACTED]

[REDACTED]

5.5 Overdose Management

An overdose is any dose of investigational study drug given to a patient or taken by a patient that exceeds the dose described in the protocol. [REDACTED]

[REDACTED] Overdoses without signs or symptoms do not need to be recorded as AEs; in case of any AEs associated with the overdose, these should be reported on relevant AE/SAE sections in the eCRF.

5.5.1 Treatment of Overdose

Treatment of suspected overdose of investigational study drugs should include investigational study drug discontinuation and implementation of appropriate supportive measures.

5.6 Blinding

The investigator will be blinded to the dose level. The volume injected will be equivalent across the doses and placebo. To ensure blinding, an appropriate and protocol-trained person at each site, such as a study nurse or other designee, will reconstitute investigational product vials in a manner blinded to the investigator and patient. [REDACTED]

[REDACTED]

[REDACTED]

[REDACTED]

[REDACTED] The designated person will then fill the syringe with the investigational product and give the filled syringe in a blinded fashion to the investigator. Appropriate spatial separation is required to ensure blinding. Blinding for the initial phase will be maintained throughout the study until the final assessment for the final patient has been entered into the database and the database lock has been performed.

5.6.1 Breaking the Blind

A patient's treatment assignment will not be broken until the end of the study unless medical treatment of the patient depends on knowing the study treatment the patient received. In the event that the blind needs to be broken because of a medical emergency, the investigator may unblind an individual patient's treatment allocation.

As soon as possible, the investigator should first contact the medical monitor to discuss the medical emergency and the reason for revealing the actual treatment received by that patient. The treatment assignment will be unblinded through IRT. Reasons for treatment unblinding must be clearly explained and justified in the eCRF. The date on which the code was broken along with the identity of the person responsible must also be documented.

5.7 Treatment Compliance

Patient compliance will be determined by capturing the precise dose administered and the time and date of dosing in the source document and the dosage administration eCRF. Delays in dosing and the reason for any delay in dosing is to be recorded on the dosage administration eCRF.

5.8 Prior and Concomitant Therapy

Use of all concomitant medications will be recorded in the patient's eCRF. The minimum requirement is that drug name, dose, and dates of administration are to be recorded. This will include all prescription drugs, herbal products, vitamins, minerals, and over-the-counter medications. Any changes in concomitant medications also will be recorded in the patient's eCRF.

Any concomitant medication deemed necessary for the welfare of the patient during the study may be given at the discretion of the investigator. However, it is the responsibility of the investigator to ensure that details regarding the medication are recorded in full in the eCRF.

6 Study Assessments and Procedures

Before performing any study procedures, all potential patients will sign an informed consent form (ICF). Patients will have the opportunity to have any questions answered before signing the ICF. The investigator must address all questions raised by the patient. The investigator or designee will also sign the ICF.

- Bin 56: 560-570 (Frequency: 100)
- Bin 57: 570-580 (Frequency: 100)
- Bin 58: 580-590 (Frequency: 100)
- Bin 59: 590-600 (Frequency: 100)
- Bin 60: 600-610 (Frequency: 100)
- Bin 61: 610-620 (Frequency: 100)
- Bin 62: 620-630 (Frequency: 100)
- Bin 63: 630-640 (Frequency: 100)
- Bin 64: 640-650 (Frequency: 100)
- Bin 65: 650-660 (Frequency: 100)
- Bin 66: 660-670 (Frequency: 100)
- Bin 67: 670-680 (Frequency: 100)
- Bin 68: 680-690 (Frequency: 100)
- Bin 69: 690-700 (Frequency: 100)
- Bin 70: 700-710 (Frequency: 100)
- Bin 71: 710-720 (Frequency: 100)
- Bin 72: 720-730 (Frequency: 100)
- Bin 73: 730-740 (Frequency: 100)
- Bin 74: 740-750 (Frequency: 100)
- Bin 75: 750-760 (Frequency: 100)
- Bin 76: 760-770 (Frequency: 100)
- Bin 77: 770-780 (Frequency: 100)
- Bin 78: 780-790 (Frequency: 100)
- Bin 79: 790-800 (Frequency: 100)
- Bin 80: 800-810 (Frequency: 100)
- Bin 81: 810-820 (Frequency: 100)
- Bin 82: 820-830 (Frequency: 100)
- Bin 83: 830-840 (Frequency: 100)
- Bin 84: 840-850 (Frequency: 100)
- Bin 85: 850-860 (Frequency: 100)
- Bin 86: 860-870 (Frequency: 100)
- Bin 87: 870-880 (Frequency: 100)
- Bin 88: 880-890 (Frequency: 100)
- Bin 89: 890-900 (Frequency: 100)
- Bin 90: 900-910 (Frequency: 100)
- Bin 91: 910-920 (Frequency: 100)
- Bin 92: 920-930 (Frequency: 100)
- Bin 93: 930-940 (Frequency: 100)
- Bin 94: 940-950 (Frequency: 100)
- Bin 95: 950-960 (Frequency: 100)
- Bin 96: 960-970 (Frequency: 100)
- Bin 97: 970-980 (Frequency: 100)
- Bin 98: 980-990 (Frequency: 100)
- Bin 99: 990-1000 (Frequency: 100)

6.2 Safety Assessments

Safety will be evaluated by frequency, severity, and duration of any adverse reactions. Adverse events will be assessed at each office visit and telephone contact.

Term	Percentage
Climate change	100
Global warming	98
Green energy	95
Carbon footprint	92
Sustainable development	88
Renewable energy	85
Emissions reduction	82
Green economy	78
Carbon tax	75

6.2.1 Adverse Events

6.2.1.1 Definitions of Adverse Events

The investigator is responsible for reporting all AEs that are observed or reported during the study, regardless of their relationship to investigational study drugs. The investigator will query the patient for changes since last visit and ask about the patient's ability to swallow.

An AE is defined as any untoward medical occurrence in a patient enrolled into this study regardless of its causal relationship to investigational study drugs. Patients will be instructed to contact the investigator at any time after randomization if any symptoms develop.

A treatment-emergent AE is defined as any event not present before exposure to investigational study drugs or any event already present that worsens in either intensity or frequency after exposure to investigational study drugs.

6.2.1.2 Serious Adverse Events

An SAE is defined as any event that

- Results in death
- Is immediately life-threatening
- Requires inpatient hospitalization or prolongation of existing hospitalization
- Results in persistent or significant disability/incapacity
- Is a congenital anomaly/birth defect

[REDACTED]

[REDACTED]

[REDACTED]

[REDACTED]

[REDACTED]

[REDACTED]

[REDACTED]

6.2.1.3 Eliciting and Documenting Adverse Events

Adverse events will be assessed from the time the patient signs the ICF until exit from the study (20 weeks after initial treatment).

Serious AEs that occur more than 90 days after the last dose of investigational study drug and the patient has exited the study need not be reported unless the investigator considers them related to investigational study drug.

At every study visit, patients will be asked a standard non-leading question to elicit any medically related changes in their well-being. They will also be asked if they have been hospitalized, had any accidents, used any new medications, or changed concomitant medication regimens (both prescription and over-the-counter medications).

In addition to patient observations, AEs identified from any study data (eg, laboratory values, physical examination findings, ECG changes) or identified from review of other documents that are relevant to patient safety will be documented on the AE page in the eCRF.

6.2.1.4 Reporting Adverse Events

All AEs reported or observed during the study will be recorded on the AE page in the eCRF. Information to be collected includes the following:

- Drug treatment
- Dose
- Event term
- Time of onset
- Investigator-specified assessment of severity and relationship to investigational study drugs
- Time of resolution of the event
- Seriousness
- Any required treatment or evaluations
- Outcome

Adverse events resulting from concurrent illnesses, reactions to concurrent illnesses, reactions to concurrent medications, or progression of disease states must also be reported. All AEs will be followed to adequate resolution. The Medical Dictionary for Regulatory Activities (MedDRA) will be used to code all AEs.

Any medical condition that is present at the time that the patient is screened but does not deteriorate should not be reported as an AE. However, if it deteriorates at any time after Screening visit, it should be recorded as an AE.

6.2.1.5 Reporting Serious Adverse Events

The sponsor or its designee is responsible for reporting relevant SAEs to the competent authority, other applicable regulatory authorities, and participating investigators, in accordance with the ICH guidelines and/or local regulatory requirements.

The sponsor is responsible for reporting unexpected fatal or life-threatening events associated with the use of the investigational study drugs (expedited reports) to the regulatory agencies and competent authorities by telephone or fax within 7 calendar days after being notified of the event. The sponsor should report other relevant SAEs associated with the use of the investigational study drugs to the appropriate competent authorities (according to local guidelines), investigators, and the institutional review board (IRB) by a written safety report within 15 calendar days of notification.

6.2.1.6 Suspected Unexpected Serious Adverse Reactions and Non-Serious Adverse Events of Special Interest

The sponsor will promptly evaluate all suspected unexpected serious adverse reactions (SUSARs) and non-serious AEs of special interest against cumulative investigational study drug experience to identify and expeditiously communicate possible new safety findings to investigators, IRBs/independent ethics committees (IECs), and applicable health authorities based on applicable legislation.

6.2.1.7 Assessment of Severity

The severity, or intensity, of an AE refers to the extent to which an AE affects the patient's daily activities. The intensity of the AE will be rated as mild, moderate, or severe using the following criteria:

Mild: An event usually transient in nature and generally not interfering with normal activities.

Moderate: An AE that is sufficiently discomforting to interfere with normal activities.

Severe: An AE that is incapacitating and prevents normal activities.

Changes in the severity of an AE should be documented to allow an assessment of the duration of the event at each level of intensity to be performed. AEs characterized as intermittent do not require documentation of onset and duration of each episode.

6.2.1.8 Assessment of Causality

The investigator's assessment of an AE's relationship to investigational study drugs is part of the documentation process, but it is not a factor in determining what is or is not reported in the study. If there is any doubt as to whether a clinical observation is an AE, the event should be reported.

The relationship or association of the test article in causing or contributing to the AE will be characterized using the following classification and criteria:

Unrelated: This relationship suggests that there is no association between the investigational study drugs and the reported event.

Possible: This relationship suggests that treatment with the investigational study drugs caused or contributed to the AE, ie, the event follows a reasonable temporal sequence from the time of drug administration or follows a known response pattern to the investigational study drugs, but could also have been produced by other factors.

Probable: This relationship suggests that a reasonable temporal sequence of the event with drug administration exists and, based upon the known pharmacological action of the drug, known or previously reported adverse reactions to the drug or class of drugs, or judgment based on the investigator's clinical experience,

the association of the event with the investigational study drugs seems likely. The event disappears or decreases on cessation or reduction of the dose of investigational study drugs.

Definite: This relationship suggests that a definite causal relationship exists between drug administration and the AE, and other conditions (concurrent illness, progression/expression of disease state, or concurrent medication reaction) do not appear to explain the event. The event reappears or worsens if the investigational study drug is re-administered.

6.2.1.9 Follow-Up of Patients Reporting Adverse Events

All AEs must be reported in detail on the appropriate page in the eCRF and followed to satisfactory resolution, until the investigator deems the event to be chronic or not clinically significant, or until the patient is considered to be stable.

6.3 Efficacy Assessments

6.3.1 TWSTRS Scale

Most studies leading to the approval of currently available botulinum neurotoxins have used the TWSTRS scale as the primary efficacy measure (Espay 2018, Fernandez 2013). The standard TWSTRS is a comprehensive scale that comprises three subsets to assess motor severity, pain, and disability (Comella 2016). The motor severity subscale consists of 10 items, with variable scaling and weighting. It also includes a disability subscale with 7 items and a pain scale with 3 items. The total score is the sum of each of the subscales. ■

6.3.2 PGI-C and CGI-C Scales

The PGI-C enables the patient to rate changes in their perception of their general health status over the duration of the assessment via a 7-point scale ranging from “very much improved” to “very much worse” (Fischer 1999). For this study, a 5-point generic PGI-C scale ranging from “much better” to “much worse” was used (FDA 2018). Similarly, the CGI-C is a 7-point scale ranging from “very much improved” to “very much worse” (Guy 1976) based on the physician’s perception of the patient’s health status. Detailed descriptions of the CGI-C and PGI-C are provided in Appendix 13.4 and Appendix 13.6, respectively.

6.3.3 PGI-S and CGI-S Scales

The PGI-S is a 1-item global index that enables the patient to rate their impression of disease severity via a 4-point scale ranging from “normal” to “severely ill” (Guy 1976). The appropriateness of the PGI-S scale used depends on the context of use (eg, patient population) (FDA 2018). For this study, a 5-point generic PGI-S scale ranging from “none” to “very severe” was used. Similarly, the CGI-S enables the clinician to rate the severity of the patient’s illness, relative to their past experience with patients who have the same diagnosis, on a 7-point scale ranging from “normal” to “among the most extremely ill patients” (Guy 1976). Detailed descriptions of the PGI-S and CGI-S are provided in Appendix 13.4 and Appendix 13.5, respectively.

6.3.4 C-SSRS

The C-SSRS was developed by the United States Food and Drug Administration (FDA) in 2012 for measuring suicidal ideation and behavior in clinical trials (Posner 2011). The C-SSRS was designed to distinguish the domains of suicidal ideation and suicidal behavior. Four constructs are measured. The first is the severity of ideation (hereafter referred to as the “severity subscale”), which is rated on a 5-point ordinal scale in which 1=wish to be dead, 2=non-specific active suicidal thoughts, 3=suicidal thoughts with methods, 4=suicidal intent, and 5=suicidal intent with plan. The second is the intensity of ideation subscale (hereafter referred to as the “intensity subscale”), which comprises five items, each rated on a 5-point ordinal scale: frequency, duration, controllability, deterrents, and reason for ideation. The third is the behavior subscale, which is rated on a nominal scale that includes actual, aborted, and interrupted attempts; preparatory behavior; and non-suicidal self-injurious behavior. The fourth is the lethality subscale, which assesses actual attempts; actual lethality is rated on a 6-point ordinal scale, and if actual lethality is zero, potential lethality of attempts is rated on a 3-point ordinal scale (Posner 2011). A detailed description is provided in Appendix 13.7.

6.3.5 Dysphagia Score

6.4 Safety Monitoring Committee

The medical monitor and sponsor will hold monthly reviews of all AEs; consequently, an independent Safety Committee will not be formed for this study.

6.5 Pregnancy

6.6 Laboratory Analyses

Any abnormal laboratory test results

[REDACTED] including those that worsen from baseline or are felt to be clinically significant in the medical and scientific judgment of the investigator, are to be recorded as AEs or SAEs.

However, any clinically significant safety assessments that are associated with the underlying disease, unless judged by the investigator to be more severe than expected for the patient's condition, are not to be reported as AEs or SAEs.

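### Protocol Sections 6.6 and 6.2.1.4 give opposite instructions on recording a worsening of the underlying disease that stays within expectation

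*Protocol*

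**What the plan says.** Section 6.6 (Laboratory Analyses) has two visible sentences on recording. The first, partly redacted, sends abnormal laboratory results to the AE or SAE record, including those that worsen or are judged clinically significant. The second qualifies it: "any clinically significant safety assessments that are associated with the underlying disease, unless judged by the investigator to be more severe than expected" for that patient's condition, "are not to be reported as AEs or SAEs".

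Four other places in the protocol address the same question.

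- Section 6.2.1.4 lists further events that have to be reported, ending with "reactions to concurrent medications, or progression of disease states must also be reported". Of a medical condition present at screening, it says that "if it deteriorates at any time after Screening visit, it should be recorded as an AE".
- Section 6.2.1.3 sends to the AE page of the eCRF "AEs identified from any study data (eg, laboratory values, physical examination findings, ECG changes" and the like).
- Section 6.2.1.8 says that the causality assessment does not decide what gets reported, and adds: "If there is any doubt as to whether a clinical observation is an AE, the event should be reported".
- Section 6.2.1.1 sets the general duty: "The investigator is responsible for reporting all AEs that are observed or reported during the study, regardless of their relationship to investigational study drugs". Its definition of a treatment-emergent AE includes an event already present that worsens after exposure.

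**The concern.** An investigator who sees a clinically significant worsening that fits the expected course of the patient's disease is told by one section to record it and by another not to. Whether it enters the database then depends on which section the site follows.

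Safety is the primary objective, and its evidence consists of recorded AEs and SAEs. Section 6.4 gives the monthly review of all AEs by the medical monitor and sponsor as the reason for having no independent safety committee, and Section 11.1.1 plans no data monitoring committee. An event kept off the AE page under 6.6 would reach neither the tables nor that review. Any loss would run one way, toward fewer recorded events. Randomization and blinding might make the loss similar across arms, but each arm's absolute proportion would still be too low.

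**Working it through.** No sample size, power or alpha figure bears on this point, and the plan states no number to reproduce. The check is a comparison of the rules, case by case, for a clinically significant finding linked to a disease present at screening.

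| Case | Section 6.2.1.4 | Section 6.6, second sentence | Result |
|---|---|---|---|
| Disease has not deteriorated | Not an AE | Not an AE or SAE | Agree |
| Deteriorated, beyond expectation for the patient | Record | Exception applies; remains reportable | Agree |
| Deteriorated, within expectation | Record | Not an AE or SAE | **Conflict** |

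The conflict is confined to the third row. It arises because 6.2.1.4 has no threshold of expectation and 6.6 has one.

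**How the other sections bear on that row.** Section 6.2.1.3 points toward recording, since it covers events found in laboratory, examination and ECG data. Section 6.2.1.8 points the same way, through its rule for doubtful cases and because it keeps the causality assessment out of the reporting decision. Section 6.2.1.1 conflicts with 6.6 only through its general duty; it does not mention disease progression. None of these sections states that it overrides 6.6.

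**Where a lost event would be missed.** Section 6.2.1.4 makes relationship to study drug one of the items collected with the AE, so an event that is never entered has no relationship assessment. The outputs directly affected are the overall TEAE summary (SAP 8.1.2), TEAE incidence (SAP 8.1.3) and serious TEAEs (SAP 8.1.6), together with the monthly review in protocol Section 6.4.

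**Reach into the primary estimand.** The primary estimand is the proportion of patients with treatment-related SAEs over 20 weeks. To be lost from it through 6.6, an event would have to meet four conditions at once:

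1. It is serious under Section 6.2.1.2.
2. It is at least possibly related to study drug.
3. It is associated with the underlying disease.
4. It is judged no worse than expected for that patient.

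Conditions 2 and 3 can hold together. The Possible category in 6.2.1.8 allows for another cause, and SAP 8.1.4 counts possible as related. Meeting all four is conceivable but narrow. The documents give no event rate from which to estimate how often it would happen.

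**The case against.** The strongest reply concerns scope. The sentence stands under a laboratory heading and opens as a qualification of the sentence before it, which is redacted just where the covered results are described. It may have been meant for laboratory values only. This stands in part: its reach beyond laboratory results is uncertain. However, the wording moves from laboratory test results to safety assessments and names SAEs, so a site could fairly read it more widely. Even on the narrow reading it conflicts with 6.2.1.3 and 6.2.1.4 for disease-associated laboratory findings.

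A second reply is that 6.2.1.8 already tells sites to report when in doubt. That helps, and it makes recording the better-supported reading. It does not remove an explicit instruction not to record, because a site following 6.6 may see no doubt to resolve.

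A third is that a reconciling sentence may lie in the redacted parts of 6.6 or 6.2.1.2. That cannot be excluded. Both conflicting sentences are nevertheless fully visible.

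Three stronger readings are tempting and are not supported.

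- A reader might infer that 6.6 bars every disease-linked finding. It does not: findings worse than expected stay reportable, and stable disease is unreported under both sections.
- A reader might infer that the primary endpoint is materially biased, and put a size on it from the effect of one missing event in a small arm. That arithmetic describes any missed event from any cause. No passage fixes the order in which 6.6 and the causality assessment are applied, and none identifies an event meeting all four conditions. Neck and shoulder pain, which the Introduction links to the disease, is not a laboratory result, and TWSTRS pain is listed under efficacy.
- A reader might infer that sites will in fact diverge and that the differences cannot even out. The text permits divergence but does not show that it will occur.

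**Conclusion.** The concern holds in a limited form. Sections 6.6 and 6.2.1.4 contradict each other for clinically significant worsening of the underlying disease that stays within expectation, and the visible text does not say which governs. Following 6.6 literally leaves out of the AE and SAE data events that 6.2.1.4 requires.

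The direct effect is on the overall TEAE and SAE tables and on the monthly AE review. An effect on treatment-related SAEs is possible but probably narrow. Neither can be quantified from the documents.

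The conclusion assumes that the underlying disease in 6.6 means cervical dystonia, or another condition present at screening, and that no redacted sentence in 6.6 or 6.2.1.2 settles the matter. If 6.6 covers laboratory results only, the conflict remains but involves fewer findings. This is an inconsistency to correct, and it does not show that the primary analysis is invalid.

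**What to change.** Reconcile 6.6 with 6.2.1.4 so that one recording rule applies. Either delete the second sentence of 6.6, or limit it to laboratory findings that were already abnormal at baseline and have not worsened. The limited version largely repeats what 6.2.1.4 already says about conditions that do not deteriorate, so deletion would lose little.

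In either case, add a statement that any event meeting the AE or SAE definition is recorded whatever its cause is thought to be, and that attribution to the disease or to study drug is captured only in the causality field. If redacted text already limits 6.6 in this way, a cross-reference from 6.2.1.4 would be enough.

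The cost is one protocol sentence, submitted as an amendment under Section 11.2.1, and matching site training text. The SAP tables keep their structure. The downside is a few more disease-related AEs on record, which the relationship tabulations in SAP 8.1.4 and 8.1.7 can already separate.
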